Univariate and multivariate regression models will be implemented to investigate the significant difference between ethnic/geographic groups in terms of prevalence and amount of damage accrual. Similarly, univariate and multivariate regression models will be implemented to investigate independent factors associated with the development or accrual of damage, as assessed by the BODI.

Multivariate Cox proportional hazards regression models will be created to assess the effect of damage (BODI score, BODI ≥ 1 , BODI ranking) on subsequent risk of death with adjustment for covariates, including gender, age, disease duration at enrollment, history of major organ involvement, disease activity at enrolment, comorbidities (onset before BS diagnosis). Results will be presented as hazard ratios with their corresponding 95% confidence intervals. Statistical significance will be defined as a P-value <0.05 . Finally, adjusted survival estimates obtained from these Cox regression models were plotted as survival curves.

Sample size

According to the results of previous studies, 95% overall 5-year survival is expected [8]. Assuming 99% and 95% of survival rate in BS patients with and without BODI damage, respectively, and assuming 50% prevalence of damage (BODI ≥ 1) in the study cohort, we estimated a required sample size of at least 801 BS patients (alpha type I error = 0.05; beta type II error 0.20) to identify damage as a predictor of mortality. Under the assumption of 25%maximum attrition (5% every year), the sample size will be increased to 1040 patients.

STUDY TIMELINE

March 2021 – June 2021: Investigators involvement and Ethic Approval (if locally required)

April 2021 – December 2021: Enrollment window

January 2022 – December 2026: Prospective follow-up window

Publication plan:

- **End of 2022 :** Publication of Cross-sectional results (*content validity*)
- **End of 2025:** Publication of mid-term results (factors associated to damage accrual)

- **End of 2028:** publication of prospective results (*construct validity*)

PUBLICATION RULES

Baseline data will be published in a peer-reviewed scientific journal within 1 year from the end of recruitment. The full results of the prospective validation will be published in a peer-reviewed scientific journal following the completion of the 5-year study. Partial or preliminary results can be published beforehand.

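### The required sample size of 801 does not follow from the inputs printed with it: usual unadjusted two-sided formulas give 564 to 666

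*Protocol*

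**What the plan says.** The Sample size section of the protocol builds its number in one paragraph.

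- Overall survival: "According to the results of previous studies, 95% overall 5-year survival is expected".
- Group rates: "Assuming 99% and 95% of survival rate in BS patients with and without BODI damage, respectively".
- Group split: "assuming 50% prevalence of damage (BODI ≥ 1) in the study cohort".
- Result: "we estimated a required sample size of at least 801 BS patients (alpha type I error = 0.05; beta type II error 0.20").
- Attrition, applied after that result: "Under the assumption of 25%maximum attrition (5% every year), the sample size will be increased to 1040 patients".

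The paragraph names no formula, sidedness or covariate allowance. The Statistical analysis section plans covariate-adjusted Cox models for death, and "Results will be presented as hazard ratios with their corresponding 95% confidence intervals". That is consistent with reading alpha as two-sided.

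**The concern.** Two event rates, a 1:1 split, alpha and beta fix the sample size up to the choice of formula, and the paragraph presents 801 as the result of those inputs. If no ordinary formula returns it, either an input is misprinted or something was used that is not printed. The stated 80% power then cannot be checked.

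This is the protocol's only sample-size justification, and the enrolment target of 1040 is built on 801. The number is tied to damage as a predictor of mortality, which is specific objective 4. The survival rates feeding the calculation also disagree with each other, so a reader cannot repair the figure by choosing a formula.

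**Working it through.** **Inputs (Sample size section).** Death risks p1 = 0.05 and p2 = 0.01, so the difference d is 0.04 and the mean risk is 0.03. Split 1:1. Alpha 0.05, taken as two-sided (z = 1.960). Beta 0.20 (z = 0.8416). (1.960 + 0.8416)² = 7.849. Sum of variances v = 0.05×0.95 + 0.01×0.99 = 0.0574. Under exponential survival the hazard ratio is ln 0.95 / ln 0.99 = 5.10.

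**Attempt to reproduce 801 at beta 0.20, with power at N = 801**

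| Method | Calculation | Total N | Power at 801 |
|---|---|---|---|
| Unpooled proportions | 2 × 7.849 × 0.0574 / 0.04² = 563.2 | 564 | 91.6% |
| Pooled proportions | 2 × [1.960√(2×0.03×0.97) + 0.8416√0.0574]² / 0.04² = 568.6 | 570 | 91.4% |
| Freedman | 7.849 × (6.10/4.10)² = 17.36 deaths; / 0.03 | 579 (600 with 18 whole deaths) | 90.9% |
| Continuity-corrected | pooled n = 284.3 per group; (n/4)[1 + √(1 + 4/(n×0.04))]² = 332.4 per group | 666 | 87.7% |
| Schoenfeld | 4 × 7.849 / (ln 5.10)² = 11.82 deaths; / 0.03 | 394 | 97.9% |
| Arcsine | 4 × 7.849 / 0.2507² = 499.6 | 500 | 94.4% |
| Log odds ratio, Wald | 2 × 7.849 × 122.06 / 1.6507² = 703.2 | 704 | 84.9% |
| Log risk ratio, Wald | 2 × 7.849 × 118 / (ln 5)² = 715.1 | 716 | 84.3% |

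The first four rows are the usual choices. 801 is 20% above the largest of them (801/666 = 1.20) and 42% above the smallest (801/564 = 1.42). It is still 12% above the largest variant tried (801/716 = 1.12). One-sided alpha lowers every figure (about 310 to 564). These ranges cover the variants tried and are not mathematical bounds.

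**Routes that do reach about 801.** Each needs an input that is not printed or that differs from the printed one.

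- Freedman at beta 0.10: 23.2, so 24 deaths; 24/0.03 = 800.
- Log odds ratio at beta 0.15: 804 before rounding to equal groups.
- Freedman with 25% attrition already included: 600/0.75 = 800. The text applies attrition after 801.
- A covariate allowance, dividing N by (1 − R²): this needs R² = 1 − 703.2/801 = 0.12 on the log odds ratio formula, 1 − 664.9/801 = 0.17 on the continuity-corrected one, or 1 − 568.6/801 = 0.29 on the pooled one.

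**Consistency of the survival inputs.** 0.5×99% + 0.5×95% = 97%, not the 95% overall. At 801 patients this means about 24 deaths (3%) or 40 deaths (5%). As printed, patients with damage have the 99% survival, although the Background says damage increases mortality. Swapping the groups changes neither N nor two-sided power at 1:1, but the level and the spread of the rates do matter. For illustration only, pairs that average 95% (assumed, none is printed) need 930 (97/93), 412 (98/92) or 232 (99/91) by the pooled formula.

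**Attrition.** 1040 × 0.75 = 780, below 801. 1040 × 0.95⁵ = 1040 × 0.7738 = 804.7, above 801. On the printed rates pooled power is 91% at 780 and 92% at 805, so this has no practical effect on power.

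**The case against.** The strongest reply is that the planned analysis is a Cox model adjusted for gender, age, disease duration, major organ involvement, disease activity and comorbidities. Several of these could correlate with damage. A modest allowance, with R² from about 0.12 to 0.29 depending on the formula, brings 801 back at 80% power, and such detail may sit in an analysis plan that is not at hand. This stands in part. It means 88-92% cannot be claimed as the power of the planned analysis, because those figures are for an unadjusted comparison. It does not rescue the paragraph, which prints no allowance and presents 801 as following from the inputs listed.

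The second reply is that the text says at least 801 and the excess is on the safe side. On the printed rates that is correct.

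A reader might infer three stronger things that the protocol does not support.

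- That the study is too small because of this discrepancy. On the printed rates every unadjusted variant gives more than 80% power at 801. Only some assumed pairs, such as 97/93, would make 801 short.
- That the authors really used 90% power. The Freedman match at 800 is a lead, and nothing in the text confirms it.
- That compounding was certainly intended for attrition. It fits 1040 better than a flat 25%, but 801/0.95⁵ is 1035, not exactly 1040, and 25% is printed as a maximum.

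**Conclusion.** The point holds as a mismatch between a printed sample size and its printed inputs. With two-sided alpha 0.05, beta 0.20 and a 1:1 split, unadjusted formulas give about 564 to 666, or 394 to 716 with less usual variants. At 801 an unadjusted comparison has about 88-92% power, or about 84-98% over all variants. The gap is conservative on the printed rates, and a covariate allowance that was not printed could account for it.

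The margin should not be relied on, because the rates behind it average 97% against a stated 95% overall. The assignment of the higher survival to patients with damage is a separate inconsistency in the same sentence, with no effect on N at 1:1. The point is of low severity: it concerns whether the justification can be reproduced, not a demonstrated loss of power.

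**What to change.** In the Sample size section:

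1. Reconcile the survival inputs: the overall rate with the two group rates at 50% prevalence, and which group has the higher survival.
2. Recompute for the planned Cox analysis. Name the method and sidedness, and state any covariate allowance.
3. Restate either the required number at alpha 0.05 and beta 0.20, or the power at the existing target of 1040 enrolled.
4. Reconcile the 25% maximum, the 5% a year and the 1040, saying whether annual loss is compounded.

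The cost is one recalculation and a rewording of one paragraph. No change in enrolment is needed.

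### The sample-size sentence equates 25% attrition with 5% per year, but the target of 1040 fits only 5% per year compounded (22.6%)

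*Protocol*

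**What the plan says.** All the figures stand in the protocol's Sample size section. The size before attrition is given as a floor: "we estimated a required sample size of at least 801 BS patients". The next sentence makes the allowance for loss: "Under the assumption of 25%maximum attrition (5% every year), the sample size will be increased to 1040 patients". That sentence gives attrition twice, as a 5-year maximum and as a yearly rate, and shows no inflation formula.

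The inputs behind 801 are survival of 99% and 95% in the two damage groups, an even split ("assuming 50% prevalence of damage (BODI ≥ 1) in the study cohort") and "alpha type I error = 0.05; beta type II error 0.20".

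Two other sections bear on what attrition means here. Statistical analysis plans Cox proportional hazards models for death. Study withdrawal says that a withdrawing patient's data are deleted if not yet published.

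**The concern.** A target inflated for attrition should leave the required number at the loss that was assumed. Here the required number is a floor, the loss is called a maximum, and 25% off 1040 falls below that floor. The sentence is also the only justification for the enrolment target and the only stated limit on acceptable loss. Someone monitoring retention would take 25% as covered, although the target holds only to a slightly smaller loss.

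**Working it through.** **Inputs (protocol, Sample size).** Required N = 801; attrition 25% maximum, also given as 5% every year; target 1040; follow-up 5 years.

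**Step 1. Reproduce 1040.** The usual inflation is N/(1 − d), where d is the cumulative loss.

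- 5% per year compounded: retained fraction 0.95^5 = 0.7738, so d = 22.6%. Then 801/0.7738 = 1035.2, so 1036. Rounded up, this is 1040. If 22.6% is first rounded to 23%, 801/0.77 = 1040.3.
- Flat 25%: 801/0.75 = 1068.
- Multiplying by 1.25 instead of dividing by 0.75 (a common slip): 801 × 1.25 = 1001.25, so 1002.

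Of these, only the compounded rate leads to 1040. The protocol does not state that it compounded; this is inferred from the fit.

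**Step 2. What 1040 retains.**

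| Reading of attrition | Cumulative loss | Retained from 1040 | Against 801 | Enrolment needed |
|---|---|---|---|---|
| 5% per year, compounded | 22.6% | 1040 × 0.7738 = 804.7 | about 4 above | 1036 |
| Flat 25% (or 5% of the starting cohort each year, 5 × 5%) | 25% | 1040 × 0.75 = 780 | 21 below | 1068 (28 more) |

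The largest loss that 1040 can absorb is 1 − 801/1040 = 23.0%.

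So 25% and 5% per year agree with each other only if the yearly losses are added, and on that reading 1040 is too small. If the losses are compounded, 1040 is right and 25% is not the cumulative figure.

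**Step 3. Size of the consequence.** Pooled two-proportion test, death risks 1% and 5%, equal groups, two-sided 0.05 (the protocol does not state sidedness). With n per group and mean risk 0.03:

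power = Φ{[0.04 − 1.96 √(2 × 0.03 × 0.97/n)] / √[(0.01 × 0.99 + 0.05 × 0.95)/n]}

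- 780 patients (n = 390): 90.7%.
- 801 patients (n = 400.5): 91.4%.

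The difference is 0.7 points. These values serve only to compare the two sizes. The same test needs about 570 patients in total for 80% power, so it does not reproduce the protocol's 801 at 80%.

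**Step 4. Is 780 the right count for the analysis?** In a Cox model, a patient lost to follow-up contributes time until censoring. If 25% were lost evenly over the 5 years (an assumption), those patients would on average contribute half their follow-up. About 87.5% of person-time would be kept, equivalent to 1040 × 0.875 = 910 full follow-ups. Only if every loss were a withdrawal with deletion of data would the analysis fall to 780 patients. The protocol does not say how attrition divides between the two.

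**The case against.** The strongest reply is that 1040 follows from an assumption written in the same sentence. Compounded, 5% per year gives 1036, rounded up to 1040, and leaves about 805. On this view 25% is a loose upper label and the enrolment number is sound. This largely stands: it shows that the protocol did inflate for attrition, and that the fault lies in equating two different losses. It does not remove the inconsistency, because a loss described as the maximum ought to be one that the target covers, and 1040 covers only 23.0%.

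A second reply is that the mortality analysis is a Cox model, not a comparison of completers, and that the protocol asks investigators to establish whether patients lost to follow-up have died (Variables, Death). This stands too, subject to the deletion rule under Study withdrawal. The count of 780 is a worst case.

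A reader might infer that the study misses its own minimum size or is underpowered, or that 28 more patients must be enrolled. The documents do not support this. The shortfall arises only on the flat 25% reading, no section limits the mortality analysis to patients who complete 5 years, and the power difference is under one point.

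**Conclusion.** The inconsistency is certain and its effect is minor. One sentence presents 25% over 5 years and 5% per year as the same assumption, and the target of 1040 is consistent with 801 only under the second, compounded to 22.6%. At a flat 25% the target retains 780 complete follow-ups, 21 (2.6%) below the floor, and 28 more enrolled patients would restore it.

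The head counts rest only on the protocol's own figures. The power comparison rests on 1% and 5% death risks, equal groups and a two-sided 0.05 test, and does not depend on which damage group has the higher risk. That 801 does not follow from its stated inputs by the same test is a separate matter. It limits what can be said about power here, but does not change the attrition arithmetic.

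**What to change.** In Sample size, replace the double description of attrition with one: *5% attrition per year, that is 22.6% cumulative over 5 years*. Show the step 801/0.95^5 = 1036, rounded up to 1040. The target then agrees with 801.

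If 25% is to remain as the maximum, say plainly that 1040 would then retain 780 complete follow-ups, below 801. Do not attach a power to 780 until the derivation of 801 has been reconciled with its inputs. Otherwise a figure of about 91% at 780 would stand beside the protocol's 80% at 801.

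The cost is one sentence. No extra enrolment is needed and no analysis changes.
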